| 10 | Distance Over-refraction and Distance Visual Acuity | 
Perform a distance spherical over-refraction OD and OS using loose lenses outside of the phoropter under ambient room illumination. The distance over-refraction may also be refined under binocular conditions. Record the results and distance visual acuity OD and OS. The results of the distance over-refraction may also be checked for the impact on near vision under monocular and/or binocular conditions.
 | |
| 11 | Determination of Lens Optimization | 
If the subjects vision is unacceptable for at least one distance or the Investigator determines that the visual acuity or over-refraction are not acceptable then a lens modification must be made.
 
Up to two attempts at changes are permitted if necessary, in order to achieve an acceptable distance and near binocular performance for the subject.
 
Follow the fitting guide allowing for at least 15 minutes of settling time between lens changes.
 | 
Appendix E (Fitting Guide)
 |

| Visit 2: Treatment1 – Optimization (If needed) | | | |
|--|--|---|-------------------------------|
| Step | Descriptor | Details | Appendix |
| 1 | Lens Optimization (if needed) | Select the reason(s) for lens change (select all that apply): 
 The settled lens rotation is such that one of the other available lens cylinder axis would be better (use LARS rule to determine the replacement lens cylinder axis) Power Modification needed Unsatisfactory Vision Other (specify reason) | |
| 2 | Lens Selection | Select the lens power, based on the Fitting Guide for each eye needing optimization. Record the test lens parameters (power and lot number). | Appendix E (Fitting Guide) |
| 3 | Lens insertion (Repeat steps 2-4 for each eye being optimized) | Subjects will insert the lens themselves. If the lens is uncomfortable, inspect for damage and remove, reinsert or replace as necessary. Damaged lenses will be stored in labeled vial with sterile saline, and clearly differentiated from the other worn lenses that will be shipped back to the Sponsor. Complete the Quality Product Complaint form. | |
| 4 | Timed settling (Repeat steps 2-4 for each eye being optimized) | The investigator will start a stopwatch as soon as the lens is inserted. Note: All lenses in this study have scribe marks at 6 o'clock and 12 o'clock positions and rotation measurements are made relative to a vertical reference line. Record base nasal or base temporal rotation to the nearest degree. At one (1) minute after insertion: Record: 1. The rotational position to the nearest degree At three (3) minutes after insertion: Record: 1. The rotational position to the nearest degree | |
| 5 | Lens settling | Allow lenses to settle at least 15 minutes. | |

| | | | |
|----|---------------------------------|---|---|
| 6 | Toric Fit Evaluation | 
After lens settling, record:
 
 • The rotational position to the nearest degree • Lens stability with blink • Lens stability with eye versions • Toric fit acceptable or unacceptable 
Toric lens fit will be unacceptable if lenses rotated more than 40 degrees, or lens stability is worse than 5 degrees movement with blink. If toric fit is unacceptable, remove the lenses, perform biomicroscopy and proceed to final evaluation.
 |  |
| 7 | Lens Fit Assessment | 
Evaluate and grade lens centration, primary gaze movement, upgaze movement and tightness (push-up test).
 
An unacceptable lens fit will be any one or more of the following:
 
 • presence of limbal exposure (appearance of clear cornea) in any gaze • presence of edge lift • Presence of unacceptable movement (excessive or insufficient) in all three movement categories (primary gaze, upgaze, and push-up). 
If either lens is deemed unacceptable, the subject will be discontinued from the study. Perform a slit-lamp evaluation and complete the Final Evaluation.
 |  |
| 8 | Determine Visual Satisfaction | 
Determine if the subject's vision is acceptable with the lenses. Allow the subject to look down a hallway or out of a window for distance vision assessments, and for them to read a book, magazine or similar for near vision.
 | |
| 9 | Distance and Near Visual Acuity | 
Distance and near Snellen visual acuity will be measured for each eye with the study contact lenses in place. For near measures use the ETDRS 2000 Series Chart 1 or Chart 2.
 
Note: The acuity will be recorded to the nearest letter OD, OS and OU.
 |  |
| 10 | Over-refraction | 
Perform a distance spherical over-refraction OD and OS using loose lenses outside of the phoropter under ambient room illumination. The distance over-refraction may also be refined under binocular conditions. Record the results. The results of the distance over-refraction may also be checked for the impact on near vision under monocular and/or binocular conditions.
 | |

| | | | |
|----|-------------------------------------|---|--|
| 11 | Additional Optimization (if needed) | Repeat steps 1-10 if an additional optimization is needed. Note: Two total attempts at optimization are permitted. | Appendix E (Fitting Guide) |
| 12 | Collection of unworn lenses | Collect unworn lenses returned by the subject when lens power has been optimized If lens power was not changed allow the subject to use the unworn lenses dispensed at Visit 1 and dispense enough lenses of the same power to last the subject until their next visit. | |
| 13 | Lens Removal | The optimized study lenses will be removed and discarded. If the lenses were not modified also remove and discard the lenses. | |
| 14 | Biomicroscopy | Perform biomicroscopy OD and OS. Slit Lamp Classification Scales will be used to grade the findings. For the conjunctival redness ([REDACTED]) 0.5 unit increments will be used in the grading. Corneal Staining Assessment ([REDACTED]) will be graded in 1.0 increments. | [REDACTED] [REDACTED] [REDACTED] |
| 15 | Insertion of Study Lenses | Provide the subject with a new set of lenses that match the distance and ADD power of the lenses that were discarded in step 13 above. Note: For lens accountability in EDC, add this new set of lenses to the total number dispensed on the Dispensing form. | |
| 16 | PRO Questionnaires | The subject will complete the PRO post-fit questionnaire. Note: Subject's Must respond to the Questionnaire in the KIOSK using their User Name and Password. | Section 16.1 |

| Visit 2: Treatment1 – Dispense2 | | | |
|---------------------------------|--------------------------------------|--|---|
| Step | Descriptor | Details | Appendix |
| 1 | Distance and Near Exit Visual Acuity | 
Distance and near Snellen visual acuity will be measured for each eye with the study contact lenses in place. For near measures use the ETDRS 2000 Series Chart 1 or 2. The acuity will be recorded to the nearest letter OD, OS and OU.
 
Note: The distance visual acuity must be at least 20/30 OU for the lenses to be dispensed.
 |  |
| 2 | Dispensing Criteria | 
The lenses will be dispensed for 6-8 days.
 
 Distance Snellen acuity equal to or better than 20/30 OU Subject must indicate that the vision is acceptable. Subject must indicate that the comfort of the lenses is acceptable. Lenses must have an acceptable toric and general lens fit. | |
| 3 | Patient Instructions | 
Instruct the Subject the following:
 
 The lenses will be worn on a daily wear basis and discarded at the end of each day. Only enough lenses will be dispensed to the subject to wear for the required number of days until their follow-up visit. No additional lenses will be dispensed. A new lens will be opened and worn each day. No cleaning or disinfecting solutions will be used. If determined necessary by the Investigator sterile non-preserved rewetting drops may be dispensed to be used as needed for dryness. Subjects will be instructed to wear lenses for a minimum of 6 hours a day, every day during the study. Subjects will be instructed to wear their glasses when not wearing the study lenses. 
Note: In the event a lens is lost or damaged, the subject will return to the investigator site for replacement. As much as reasonably possible, a damaged lens should be returned to the investigational site and then returned to the Sponsor. If lens damage is present, complete the Product Quality Complaint Form. The lens will be stored in labeled vial with sterile saline, and returned to the Sponsor.
 | |
| 4 | Follow-up | 
The subject will be scheduled to return for their follow-up appointment in 7±1 day.
 | |

Subjects must report to the visit wearing the study lenses

| Visit 3: Treatment1 – FollowUp2 | | | |
|---------------------------------|---|--|---|
| Step | Descriptor | Details | Appendix |
| 1 | Concomitant Medication and Medical History Review | Confirm if there have been any changes in concomitant medications or health status since the last visit. | |
| 2 | Wear Time | Record the average hours the subject has worn the study lenses and the comfortable wear time. | |
| 3 | Compliance | Record compliance with the required wear time. Subjects must have worn lenses for at least 6 hours per day. Note: To be counted as a day of wear at this visit the Subject must have worn the study lenses for 6 hours prior to the visit. | |
| 4 | Collection of Unworn lenses | If there are any unworn study lenses collect them from the subject. | |
| 5 | PRO Questionnaires and CLDEQ 8 | The subject will evaluate the vision characteristics, comfort characteristics, handling characteristics, and visual symptoms of the study lenses using the PRO questionnaires. Note: Subject's Must respond to the Questionnaire in the KIOSK using their User Name and Password | Section 16.1 |
| 6 | Ocular Symptoms | If the subject reports ocular symptoms with the study lenses they will be recorded in the Subject Reported Ocular Symptom Questionnaire. |  |
| 7 | Subjective Acceptance | Record whether the subjects distance and near vision with the lenses is acceptable. | |
| 8 | Distance and Near Entrance Visual Acuity | Distance and near Snellen visual acuity will be measured for each eye with the study contact lenses in place. For near measures use the ETDRS 2000 Series Chart 1 or Chart 2. Note: The acuity will be recorded to the nearest letter OD, OS and OU. | |
| 9 | Binocular Distance Over-refraction and Distance Visual Acuity | Perform a binocular over-refraction and record the OD and OS results and distance visual acuity. Note: No lens changes are allowed based on the over-refraction. | Appendix D |

| | | | |
|----|--|---|---|
| 10 | Toric Fitting Assessment | 
Record the toric fit of the study lenses:
 
 • The rotational position to the nearest degree • Lens stability with blink • Lens stability with eye versions • Toric fit acceptable or unacceptable 
Toric lens fit will be unacceptable if lenses rotated more than 40 degrees, or lens stability is worse than 5 degrees movement with blink.
 |  |
| 11 | Lens Fit Assessment: | 
Evaluate and grade lens centration, primary gaze movement, upgaze movement and tightness (push-up test).
 
An unacceptable lens fit will be any one or more of the following:
 
 • Presence of limbal exposure (appearance of clear cornea) any gaze • Presence of edge lift • Presence of unacceptable movement (excessive or insufficient) in all three movement categories (primary gaze, upgaze, and push-up). |  |
| 12 | Visual Performance Distance (3M) Intermediate (64cm) Near (40cm) | 
Visual performance will be recorded OD, OS, and OU for the following:
 
Distance, Bright Illuminance ETDRS Charts 3M-HC#1, HC#2, HC#3 and LC#1, LC#2 and LC#3
 
Near, Bright Illuminance Reduced Guillon-Poling charts High Contrast and Low Contrast Intermediate (64cm) and Near (40cm).
 
Distance, Dim Illuminance (with Distance goggles) ETDRS Charts 3M-HC#4, HC#5, HC#6
 
Near, Dim Illuminance (with Near goggles) Reduced Guillon-Poling charts High Contrast Intermediate (64cm) and Near (40cm).
 
Note: The room illuminance must be between 7.3 and 7.9 EV. Distance, HC-1 Chart luminance Acceptable EV Range 10.5-10.7. Guillon-Poling, Near Chart luminance Acceptable EV Range 10.8-11.1. Do not use the Mesopic filter for Dim luminance (Dim luminance will be simulated by using the goggles)
 |  |

| | | | |
|----|----------------|---|--|
| 13 | Questionnaires | The subject will answer the product concept questions. Note: Subject's Must respond to the Questionnaire in the KIOSK using their User Name and Password | |
| 14 | Lens Removal | Have the Subject remove the study lenses and save in sterile saline in glass labeled vials, detailing the study number, subject number, subject global ID, date, eye the lens was worn on, and time of lens wear (in hours). | |
| 15 | Biomicroscopy | Perform biomicroscopy OD and OS. Slit Lamp Classification Scales will be used to grade the findings. For the conjunctival redness in CTP 2002 0.5 unit increments will be used in the grading. Corneal Staining Assessment [REDACTED] will be graded in 1.0 increments. | [REDACTED] [REDACTED] [REDACTED] |

| Step | Descriptor | Final Evaluation | Appendix |
|------|---|---|--------------|
| 1 | Distance Subjective Sphero-cylindrical Refraction and Distance Exit Visual Acuity | An optimal, binocular balanced distance sphero-cylindrical refraction will be performed. Record the refraction and distance visual acuity to the nearest letter. | [REDACTED] |
| 2 | Subject Interviews (PRA clinic only) | Subjects at the PRA clinic will be interviewed with regards to their experience with the study lenses. | Section 16.1 |
| 3 | Subject Disposition | Indicate the subject completed the study successfully or not. For subjects who discontinue, indicate the reason. | |

4.8 DISCONTINUATION CRITERIA

Johnson & Johnson Vision Care, Inc. reserves the right to terminate the study at any time for any reason. Additionally, the IRB/IEC reserves the right to terminate the study if an unreasonable risk is determined. The study may be terminated by the Principal Investigator or Medical Monitor due to specific clinical observations, if in their opinion it would be unwise to continue.

Johnson & Johnson Vision Care, Inc. will evaluate all adverse events. If it is determined that an adverse event presents an unreasonable risk, the investigation, or that part of the investigation presenting the risk, will be terminated, as soon as possible.

Should the study be terminated (either prematurely or as scheduled), the Investigator will notify the Institutional Review Board (IRB), and Regulatory Authority as required by local regulatory requirements.

4.9 ACCOUNTABILITY PROCEDURES FOR INVESTIGATIONAL PRODUCT AND CONTROL

Johnson & Johnson Vision Care, Inc. will provide the Investigator with sufficient quantities of study articles and supplies to complete the investigation. The Investigator is asked to retain all lens shipment documentation for the test article accountability records. The Investigator may provide the subject additional lenses in the event a lens is damaged or lost between visits.

Test articles must be kept in a locked storage cabinet, accessible only to those assigned by the Investigator for dispensing. All investigational products must be accounted. This includes 1) what was dispensed for the subject to wear out of the office or issued for the subject to replace appropriately between visits, 2) what was returned to the Investigator unused, and 3) the number and reason for unplanned replacements. The Investigator may delegate this activity to an authorized study site staff member on the Delegation Log.

The Investigator will collect all unused test articles from the subjects at the end of the subject's participation. Following final reconciliation of test articles, the Investigator will package and return all unused study articles to JJVC.

Reference APPENDIX A: TEST ARTICLE ACCOUNTABILITY IN THE EDC SYSTEM for additional instructions.

4.10 PROCEDURES FOR MAINTAINING AND BREAKING RANDOMIZATION CODES

The study lenses will be labeled using lens codes. It is not possible to mask the subjects as to the prescription type (i.e. astigmatism, spherical, multifocal) however the partial masking will occur as the subjects will not be informed of the identity of the test lens. The study lens mask shall not be broken unless information concerning the lens type is necessary for the urgent medical treatment of a subject. The Sponsor should be notified before the mask is broken.

As the study is a single ARM study there is no randomization.

4.11 REPORTING PRODUCT QUALITY COMPLAINTS

A Product Quality Complaint (PQC) refers to any written, electronic, or oral communication that alleges deficiencies related to the identity, quality, durability, reliability, safety, effectiveness or performance of test articles after they have been released for clinical trial use. A PQC is associated with any investigational product (i.e. product manufactured or supplied specifically for a clinical trial).

Complaint Handling

Once site personnel have become aware that a PQC has occurred, it shall then be recorded in the EDC system, which triggers an automatic email notification to the appropriate COM/CRA and Clinical QA representative. In cases where the EDC system in use is not configured to send automatic notifications, then the COM/CRA is responsible for notifying Clinical QA upon discovery that a PQC has occurred.

Upon receipt of the EDC notification the COM/CRA shall complete the applicable sections of the Product Quality Complaint Form [REDACTED]

For each complaint, the following minimum information shall be recorded by the CRA/COM on the Product Quality Complaint Form [REDACTED]

- Date the complaint was received/recorded in the EDC System (Date of Sponsor Awareness)
- Who received the complaint
- Study number
- Investigational site information (contact name, site ID, telephone number)
- Lot number(s)
- Unique Subject Identifier(s)
- Indication of who first observed complaint (site personnel or subject)
- OD/OS indication, along with whether or not the lens was inserted
- Any related AE number if applicable
- Detailed complaint description (scheduled/unscheduled visit, wear time, symptoms, resolution of symptoms, etc.)
- Eye Care Provider objective (slit lamp) findings if applicable
- Confirmation of product availability for return (and tracking information, if available), or rationale if product is not available for return [REDACTED]

Clinical QA will assign a unique number to the PQC. Complaint numbering is assigned as follows:

RDTC-XX-001, where RDTC = R&D Technical Complaint, XX = last two digits of the current year, 001 = sequential numbering starting with 001.

5.1 WITHDRAWAL CRITERIA

A subject will be withdrawn from the study for any of the following reasons:

- Lost to follow-up
- Withdrawal of consent
- Death
- Discontinuation of study treatment as a result of the investigator's clinical judgment that for safety reasons (e.g., adverse event) it is in the best interest of the subject to stop treatment.
- The subject becomes pregnant.

For discontinued subjects, the Investigator will:

- Update the enrollment log to document reason for discontinuation
- Complete the "last" Follow-up Visit form (scheduled or unscheduled)
- Complete the Final Evaluation form, indicating the reason that the subject was discontinued from the study
- Record the spherocylindrical refraction with best corrected distance visual acuity
- Collect used study lenses and test articles (worn or brought to the visit) from the subject and return to JJVC
- Collect all unused study lenses and test articles from the subject and return to JJVC

Subjects becoming pregnant during the study will be discontinued. Once discontinued, pregnant participants and their fetuses will not be monitored for study related purposes. At the Investigators' discretion, the study

participant may be followed by the Investigator through delivery. However, this data will not be collected as part of the clinical study database. Pregnant participants are not discontinued from contact lens or solution related studies for safety concerns, but due to general concerns relating to pregnancy and contact lens use. Specifically, pregnant women are discontinued due to fluctuations in refractive error and/or visual acuity that occur secondary to systemic hormonal changes, and not due to unforeseen health risks to the mother or fetus.

In cases where a subject is lost to follow-up, every possible effort must be made to contact the subject and determine the reason for discontinuation / withdrawal. The measures taken to follow up must be documented including two written attempts and a certified letter as the final attempt.

6.1 PRESTUDY AND CONCOMITANT THERAPY

Concomitant medications will be documented during screening and during the study. Disallowed medications for this study include: use of medications that contraindicate contact lens wear. Concomitant therapies that are disallowed include: therapies in which contact lens wear is contraindicated.

6.2 MONITORING TREATMENT COMPLIANCE

Johnson & Johnson Vision Care, Inc. representatives or designees will monitor the study in a manner consistent with ICH GCP E6. The study monitors will maintain close contact with the Principal Investigator and the Investigator's designated staff. The monitor's responsibilities will include:

- Ensuring that the investigation is being conducted according to the protocol
- Ensuring the rights and wellbeing of subjects are protected
- Ensuring that protocol deviations are documented with corrective action plans, as applicable
- Ensuring that the site has sufficient test article and supplies
- Clarifying questions regarding the study
- Resolving study issues or problems that may arise
- Reviewing the study records to ensure completeness and accuracy
- Study and subject source document records reviewed will include:
 - The Information and Consent Form per 21CFR Parts 50 and 56 and the HIPAA documents
 - Source documentation including consenting and HIPAA process, medical history, concomitant medications, and adverse event information as applicable. The source document should be initialed and dated by the study investigator/s.
 - Investigational product shipping, dispensing, accountability, and return/destruction records
 - Study related Regulatory documents as per ICH E3 section 8

Monitoring for this study will be specified in the monitoring plan which will be provided separately.

6.3 UNSCHEDULED VISITS

If, during the investigation, a subject experiences any investigational device-related difficulties and/or problems requiring an unscheduled visit to the clinic, the following information will be collected at a minimum:

- Chief complaint prompting the visit. If the reason is an adverse event, the applicable eCRF for the adverse event should be completed and source documentation completed as appropriate.
- Date and time of the visit and all procedures completed at the unscheduled visit

- Review of adverse event and concomitant medications
- Documentation of any investigational product dispensed or collected from the subject.
- Slit lamp findings (using the Slit Lamp Classification Scale)

If the Investigator withdraws a subject from the study, the final study visit case report forms must be completed indicating the reason(s) why the subject was withdrawn. The subject enrollment log should be completed documenting the date and primary reason for withdrawal and the study CRA notified.

Any investigational device-related difficulties and/or problems that are ongoing at the time of the final study visit will be followed by the Investigator, within licensure, until they have returned to pre-treatment status, stabilized, or been satisfactorily explained. If further treatment (i.e., beyond licensure) is required, the subject will be referred to the appropriate health care provider.

7.1 EFFICACY PARAMETERS

The efficacy parameter in this study is subjective assessment of quality of vision after wearing the optimized study lenses for 12 to 16 days.

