1.8 PROTOCOL SYNOPSIS

| |
|---|
| Protocol Number and Title: CR-5903 Evaluation of a Novel Toric Multifocal Contact Lens in Hyperopic Presbyopes |
| Sponsor: JJVC, [name] |
| Investigational Products: Investigational Toric Multifocal Contact Lens for Presbyopia |
| Ancillary Supplies: ETDRS Light Box, Near Guillon-Poling Charts, Near Lamps, Guillon-Poling Chart Holder, Pupillometer, Rewetting drops, saline solution for final lens storage, and lens cases. |
| Randomization and Dispensing: Single Arm,(Non- Randomized) Dispensing trial |
| Microbiology or Other Testing Laboratory: Not Applicable |
| Phase or Type of Study: Feasibility |

Primary Objective: To evaluate the subjective feedback of a multifocal contact lens in a population of presbyopes with hyperopia.

Secondary Objectives:

- 1 – Evaluate the fit of the toric multifocal lens.
- 2 – Evaluate the ocular physiological response of the toric multifocal lens.

Study Design: This is a single-masked, single-arm, dispensing feasibility study. There will be three study visits. Visit 1 will include baseline measurements and screening to ensure eligibility. Eligible subjects will be fit in study lenses and dispensed for 6-8 days. At Visit 2 additional measurements will be performed and it will be determined if lens optimization is required and lenses dispensed for an additional 6-8 days. At Visit 3 the primary endpoint data used for analysis will be collected. The lenses will be worn as a daily disposable.

Sample Size: A total of approximately 60 eligible subjects will be enrolled into the study with 48 subjects targeted to complete. An attempt will be made to evenly distribute the subjects across the following ADD groups and ATR & WTR.

Distribution of the 48 Completed Hyperopes will be 24 ATR and 24 WTR

| +0.75 to +1.50 ADD | | +1.75 to +2.50 ADD | |
|-----------------------|-----|--------------------|-----|
| ATR | WTR | ATR | WTR |
| ≈12 | ≈12 | ≈12 | ≈12 |

Screening: Healthy male and female volunteers (from 40 to 70 years of age) with a need for presbyopic correction in both eyes will be screened as per criteria outlined below.

Qualification, Dispensing and Follow-Up Procedures:

Screening: Subjects will complete informed consent. Demographics and medical history will be reviewed and baseline measurements completed. Subjects must meet all of the study inclusion criteria to continue in the study.

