2.4 DESCRIPTION OF TRIAL TREATMENTS

The test lens trial treatment will consist of the Investigational Toric Multifocal (ITM) lenses being fit in both eyes. The study lens system will be worn for approximately 12-16 days with a 6-8 day optimization visit.

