4.1 PRIMARY AND SECONDARY ENDPOINTS

The primary endpoint is overall quality of vision assessed using the Contact Lens User Evaluation questionnaire (CLUE™). CLUE is a validated Patient Reported Outcome (PRO) questionnaire developed to measure general and throughout the day comfort/vision, as well as symptoms of discomfort/poor vision, lens handling and packaging. Derived CLUE scores using Item Response Theory (IRT) follow a normal distribution with a population average score of 60 (SD 20), where higher scores indicate a more favorable/positive response. A 5 point increase in an average CLUE score translates into 10% shift in the distribution of scores for population of soft contact lens wearers.

The following one (1) primary hypothesis will be tested throughout this investigation. The primary hypothesis must be met to satisfy the objective of the study.

Primary Study Hypothesis

| | |
|---|--|
| 1 | After 12 to 16 days of wear, the CLUE vision score of the test lens will be non-inferior to subjects' habitual lens using a margin of -5 points. |
|---|--|

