4.4.1 TIME AND EVENT SCHEDULE

Visit 1 (Day 0)

Statement of Informed Consent
Demographics
Medical History/Concomitant Medications
Current Contact Lens Brand/Modality/Type of Correction
Contact Lens History
Wear Time with Habitual Lenses
Screening Eligibility
Baseline PRO Questionnaire and CLDEQ-8
Ocular Symptoms
Distance and Near Entrance Visual Acuity
Visual Performance
Binocular Over-Refraction
Lens Removal
Pupillometry
Keratometry
Subjective Refraction and Distance Visual Acuity
Add Determination
Ocular Dominance
Near Add Refinement
Near Visual Acuity
Biomicroscopy
Baseline Eligibility
Lens Selection
Right Lens Insertion
Lens Damage
1 Minute Rotation Measurement
3 Minute Rotation Measurement
Left Lens Insertion
Lens Damage
1 Minute Rotation Measurement
3 Minute Rotation Measurement
15 Minute Settling Time
Toric Fit Assessment
Subjective Lens Fit Assessment
Visual Satisfaction
Study Lens Distance and Near Visual Acuity
Distance Over-refraction and Distance Visual Acuity
Modification (if required)
PRO Post-Fit Questionnaire
Manual Misrotation Base Nasal (Right Eye Only)
Manual Misrotation Base Temporal (Right Eye Only)
Manual Misrotation Base Nasal (Left Eye Only)
Manual Misrotation Base Temporal (Left Eye Only)
Distance and Near Exit Visual Acuity
Dispensing Criteria

Patient Instructions
Scheduling for Follow-up 6-8 days

VISIT 2 (6-8 Days after Visit 1)

Confirm Medical History
Wear Time
Compliance
PRO Questionnaire
Ocular Symptoms
Subjective Acceptance
Entrance Distance and Near Visual Acuity
Toric Fit Assessment
Subjective Lens Fit Assessment
Distance Over-Refracton and Distance Visual Acuity
Lens Optimization (if needed)
Lens Selection (if needed)
Lens Insertion (if needed)
Lens Damage (if needed)
1 Minute Rotation Measurement (if needed)
3 Minute Rotation Measurement (if needed)
15 Minute Settling Time (if needed)
Toric Fit Assessment (if needed)
Subjective Lens Fit Assessment (if needed)
Visual Satisfaction (if needed)
Study Lens Distance and Near Visual Acuity (if needed)
Distance Over-Refracton and Distance Visual Acuity (if needed)
Additional Optimization (if needed)
Unworn Lens Collection (if lenses are optimized)
Lens Removal
Biomicroscopy
Insertion of Study Lenses
PRO Post-Fit Questionnaires
Distance and Near Exit Visual Acuity
Dispensing Criteria
Patient Instructions
Scheduling for Follow-up 6-8 day

Visit 3 (6-8 days from Visit 2)

Confirm Medical History
Wear Time
Compliance
Unworn Lens Collection
PRO Questionnaires and CLDEQ 8

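### Does changing lenses at Visit 2 make the section 7.1 efficacy parameter unmeasurable, because the final lens is worn for only 6-8 days?

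*Combined protocol and SAP*

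**What the plan says.** Section 7.1 states the efficacy parameter in one sentence: "subjective assessment of quality of vision after wearing the optimized study lenses for 12 to 16 days".

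Section 4.1 states the primary hypothesis: "After 12 to 16 days of wear, the CLUE vision score of the test lens will be non-inferior to subjects' habitual lens", with a margin of -5 points. It speaks of the test lens and does not say optimised.

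The synopsis (section 1.8, Study Design) sets the sequence. First, "Eligible subjects will be fit in study lenses and dispensed for 6-8 days". Then, at Visit 2, "it will be determined if lens optimization is required and lenses dispensed for an additional 6-8 days". Finally, "At Visit 3 the primary endpoint data used for analysis will be collected". The schedule in section 4.4.1 places Visit 3 at 6-8 days after Visit 2 and marks the optimisation steps as conditional.

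Section 2.4 says that the lens system is "worn for approximately 12-16 days with a 6-8 day optimization visit". The dispensing paragraph of section 1.8 and the opening of section 4.4 also give 12-16 days for study-lens wear as a whole.

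**The concern.** Read literally, section 7.1 requires 12-16 days in a lens that, for some subjects, is chosen only halfway through that period. Those subjects rate a prescription worn for 6-8 days, while subjects who needed no change rate one worn for 12-16 days. The analysis in section 9.1 pools the two groups and has no term for a change at Visit 2.

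Two things would be at stake. The report could credit the optimised lens with about twice the wear that some subjects had. The single estimate would also average two exposure groups in proportions that the plan does not state. If section 7.1 governed the primary endpoint, the planned visits could not deliver it for anyone refitted at Visit 2.

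**Working it through.** **Inputs**

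- Visit 1 to Visit 2: 6-8 days (sections 1.8 and 4.4.1).
- Visit 2 to Visit 3: 6-8 days (sections 1.8 and 4.4.1).
- Primary score: Visit 3 (section 1.8). In section 4.7.1 the Visit 3 questionnaires come before the over-refraction, and no lens change based on it is allowed, so the lens rated is the one dispensed at Visit 2.
- Stated exposure: 12-16 days (sections 1.8, 2.4, 4.1, 4.4 and 7.1).

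**Reproducing the plan's figure**

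Total wear = first period + second period. Minimum: 6 + 6 = 12 days. Maximum: 8 + 8 = 16 days. The stated 12-16 days is therefore total study-lens wear.

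**Wear of the final prescription at the primary score**

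- Changed at Visit 2: second period only, 6-8 days.
- Not changed at Visit 2: both periods, 12-16 days. Section 4.7.1 (Visit 2, Optimization, step 12) keeps these subjects on the same power.

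The proportion changed, p, is not given, so take it as anything from 0 to 1. With period midpoints of 7 and 14 days, mean wear of the final prescription is 14(1 - p) + 7p = 14 - 7p:

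| p | Mean days in final prescription |
|---|---|
| 0 | 14 |
| 0.5 | 10.5 |
| 1 | 7 |

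Mean wear of the study lens as a product is 14 days at every p.

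**What changes in the analysis**

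Set the two readings side by side. Whether 12-16 days means total wear or wear of the final prescription, section 9.1 fits the same mixed model to the same baseline and follow-up scores. It compares the lower 95% limit of follow-up minus baseline with -5. The sample-size table in section 9.2 uses an assumed difference, an SD of 19 and a power of 0.9; wear time is not an input. Neither the estimate nor the test depends on which reading is taken.

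**Would a model term for Visit 2 change help?**

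Take the most favourable case, an even split of the 48 completers (24 and 24), and assume the section 9.2 SD of 19 applies to the change score in each group. The standard error of the difference between groups is 19 × √(1/24 + 1/24) = 19 × 0.2887 = 5.48 points. The 95% half-width is about 1.96 × 5.48 = 10.7 points, more than twice the 5-point margin. Any other split is less precise.

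**The case for a change.** The best case for acting rests on the protocol's own vocabulary and on how lens changes are triggered. Section 4.4.1 calls the Visit 1 step a modification and the Visit 2 step an optimisation. On that usage, subjects in optimised lenses are exactly those with 6-8 days of wear, and those with 12-16 days in one prescription were never optimised. Section 4.7.1 also requires a change at Visit 2 when the subject's vision is unacceptable at one or more distances, or when the investigator finds the acuity or over-refraction unacceptable. The two groups therefore differ in a way tied to the outcome, and a pooled result does not separate first-fit success from refitting.

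Part of this stands. The sentence in section 7.1 does not fit a subject changed at Visit 2, and anyone reading it alone would be misled about exposure.

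The rest does not carry. The vocabulary is not strict: section 4.7.1 also calls the Visit 2 change a modification. Up to two modifications are allowed at Visit 1, so an unchanged subject may have worn an already refined prescription throughout. A Visit 2 change selects another parameter of the same product, possibly in one eye only. Lenses are replaced daily, so no physical lens is worn for 12-16 days in any case.

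The dependence of lens changes on vision also counts against modelling change status. It arises after baseline and is driven by the outcome, so an interaction with time would mix wear duration, fitting difficulty and the new prescription, and could not isolate duration. Fitting, refining once if needed and scoring at the end is a coherent strategy to evaluate in a single-arm feasibility study, and sections 1.8 and 2.4 describe it openly.

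**Conclusion.** The concern does not call for a change. The arithmetic is correct: a lens first dispensed at Visit 2 has 6-8 days of wear at the primary score, against the 12-16 days in section 7.1. That makes one word in a one-sentence summary a clerical slip. It does not make the endpoint unmeasurable. Sections 1.8, 2.4, 4.1 and 4.4 agree on 12-16 days of study-lens wear, the schedule delivers it, and the synopsis fixes the score at Visit 3. An analyst following the plan has one natural course and reaches the same estimate, interval and conclusion under either reading.

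The effect on the primary result is nil. The effect on description is at most a factor of two in days worn of the final prescription, for an unknown share of subjects. Reasons for change and new lens parameters are recorded at Visit 2, so the report can count these subjects without any amendment.

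This rests on two assumptions: that the hypothesis in section 4.1 governs over the summary in section 7.1, and that the test lens means the investigational product across its powers and axes, as sections 2.1 and 2.4 describe it. Nothing in the documents suggests that 6-8 days is too short to rate vision in a refined prescription. If evidence to that effect existed, it would bear on the visit schedule, which the concern leaves alone.
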